1. OBJECTIVES

1.1 Study Design

The study is an open label, phase I trial in which patients with high-risk melanoma will be immunized with up to 20 peptides that are both specific to the patient's tumor cells (i.e. – not found in their normal cells) and unique to the patient (i.e. – “personal”). These peptides are encoded by missense mutations, in-frame gene fusions and novel open reading frame mutations (collectively known as “neoantigens”) that have occurred within that patient's tumor cells and are identified through DNA and RNA sequencing. Up to 20 peptides about 20-30 amino acids in length will be prepared for each patient and will be administered together with the immune adjuvant poly-ICLC. Thus, the personalized NeoAntigen Cancer Vaccine consists of peptides + poly-ICLC and will be termed “NeoVax”.

Eligible patients will be initially entered into the trial to undergo surgery with the intent to resect all melanoma detectable clinically and on radiographic scans. Patients will be reassessed for eligibility prior to the first vaccination and will continue onto the treatment phase of the trial if secondary eligibility criteria are met.

Five patients will be entered for the initial safety evaluation (Cohort 1). If none or only 1 patient experiences a DLT on Cohort 1, an additional 10 patients will be treated at this dose to increase the likelihood of detecting serious toxicities, to complete biologic correlative endpoints and to gain preliminary experience with clinical tumor activity. If two or more patients in Cohort 1 experience dose limiting toxicity (DLT) during the first 7 weeks of treatment, then the dose of poly-ICLC will be reduced by 50% and 5 patients will be enrolled on Cohort -1. If none or only 1 patient experiences a DLT on Cohort -1, then an additional 10 patients will be enrolled as described above. If two or more patients in Cohort -1 experience a DLT, then the study will be stopped.

In parallel and under the same IND (#15703), a second phase I trial is being conducted with NeoVax (DF/HCC # 14-362 - A Phase I Study of a Personalized NeoAntigen Cancer Vaccine with Radiotherapy Among MGMT Unmethylated, Newly Diagnosed Glioblastoma Patients). Both trials utilize early stage patients who are otherwise healthy with competent immune systems. For both trials, the NeoVax personalized peptides are being produced by the same process and released to the same specifications, identical amounts are being used and the identical amount of Hiltonol® is added. In both trials the vaccination schedule is identical and the definition of Dose Limiting Toxicities is identical. In both trials, an initial cohort of five patients is being evaluated for safety.

For the purposes of evaluation of safety in the five patient cohort for either trial, the initial patients from both trials will be combined to achieve the required 5 patient cohort. Once 5 patients from the combined trials have successfully reached the end of the DLT evaluation window (4 weeks after the last priming dose) and if fewer than two DLTs have been observed, treatment can initiate to complete the initial 5 patient cohort and for the additional 10 patients at the selected dose.

CONFIDENTIAL

This document is confidential. Do not disclose or use except as authorized.

The primary objectives of the study are to test the safety and feasibility of administering NeoVax; the secondary objectives include evaluating the immune response to the personalized neoantigens and monitoring disease recurrence.

1.2 Primary Objectives

- 1.2.1** To evaluate safety and tolerability of administering NeoVax in patients with high-risk melanoma
- 1.2.2** To determine the feasibility of generating and administering NeoVax in patients with high-risk melanoma

Two feasibility endpoints will be evaluated:

- (1) The proportion of patients for whom sequencing and analysis leads to identification of at least 10 actionable peptides to initiate vaccine production
- (2) The proportion of patients for whom the time between surgery and vaccine availability is 12 weeks or less (excluding those patients who did not generate at least 10 actionable peptides)

1.3 Secondary Objectives

- 1.3.1** To assess the induction of specific cellular immune responses following administration of NeoVax
- 1.3.2** To determine the proportion of patients alive without progression at two years after surgery following administration of NeoVax

2 BACKGROUND

2.1 Study Agents

2.1.1 Personalized NeoAntigen Peptides

Sequencing technology has revealed that each tumor contains multiple, patient-specific mutations that alter the protein coding content of a gene¹. Such mutations create altered proteins, ranging from single amino acid changes (caused by missense mutations) to addition of long regions of novel amino acid sequence due to frame shifts, read-through of termination codons or translation of intron regions (novel open reading frame mutations; neoORFs). These mutated proteins are valuable targets for the host's

CONFIDENTIAL

This document is confidential. Do not disclose or use except as authorized.

immune response to the tumor as, unlike native proteins, they are not subject to the immune-dampening effects of self-tolerance. Therefore, mutated proteins are more likely to be immunogenic and are also more specific for the tumor cells compared to normal cells of the patient².

There have been several reports indicating that tumors expressing missense mutations or neoORFs can be prevented, and in some cases eradicated, by immunization with peptides corresponding to the mutated protein³⁻⁷. For example, CD8⁺ cytotoxic T lymphocytes (CTLs) directed at missense mutations in the RNA helicase protein⁶ or the β2-spectrin protein⁸ found in particular murine tumors have been identified. Expression of these mutated proteins by the tumor was found to correlate with tumor control or progression.

Correspondingly, several human studies of spontaneous regression and long-term survival have shown that powerful CD8⁺ T cell responses against mutated epitopes correlate with good clinical responses⁹⁻¹². These observations were made in both melanoma and lung cancer. Most of these CD8⁺ T cell responses show specificity toward the mutated missense epitope compared to the native epitope, represent a high proportion of circulating T cells, and result in cells that are more abundant and active than CD8⁺ T cell responses in the same patients directed toward over-expressed native antigens.

Two studies in humans have directly assessed the immunotherapeutic potential of mutated antigens. Follicular lymphoma is characterized by uncontrolled growth of a B cell expressing rearranged immunoglobulin. Purification of that rearranged immunoglobulin and use as a vaccine may improve disease-free survival¹³. The induced CD8⁺ T cells showed reactivity to the rearranged, mutated portion of the immunoglobulin molecule (the idiotype) and not the germline framework¹⁴. Moreover, a mix of peptides corresponding to the oncogenic proteins of HPV (a neoORF for humans) has been shown to result in significant remission of premalignant lesions induced by HPV¹⁵⁻¹⁷.

Thus, in animals and in humans, immune responses to both discrete mutated antigens (such as missense mutations) and expansive novel antigen (neoORF) are observationally correlated with regression and long-term remission and, in two cases, were shown to control disease following immunization. Importantly, escape from host immunosurveillance (“immunoediting”) can be tracked to alterations in expression of dominant mutated antigens in mice^{8,18} and man¹⁹.

Most cancer vaccines employing peptides as immunogens have utilized “short” peptides. These peptides are typically 9 – 10 amino acids in length and capable of direct binding to the HLA molecule on the surface of HLA-expressing cells. “Long” peptides, ~20-30 amino acids in length, have recently been shown to produce a more robust and more durable immune response^{15,16}. Long peptides require internalization, processing and cross-presentation in order to bind to HLA molecules; these functions

CONFIDENTIAL

This document is confidential. Do not disclose or use except as authorized.

only occur in professional antigen-presenting cells, such as dendritic cells, which can induce strong T cell responses.

Many studies in humans have demonstrated the safety of peptide vaccines. These include studies with multiple short peptides³³ as well as multiple long peptides, including neoORFs. In particular, two studies have been conducted with a mixture of 10 overlapping long peptides derived from p53^{28,29} and three separate studies with a mixture of 13 long peptides derived from the oncogenic proteins of HPV¹⁷⁻¹⁹. In these studies, no toxicity higher than grade 2 was observed and most adverse events were of limited duration and severity. Additionally, many heterologous antigen preparations have been tested in humans. Such preparations include irradiated cell vaccines^{20,21} and tumor cell lysates²². These heterogeneous vaccines contain mutated antigens, in the form of intact proteins, partially degraded intracellular protein, and peptides found on the surface bound to MHC I. Moreover, they contain over-expressed and selectively-expressed molecules as well as many additional native proteins. In addition, purified heat shock protein (HSP) 96 peptide complexes have been used as antigen²³; such complexes also contain many mutated peptides. None of these studies have reported significant safety issues directly attributable to the immunogens of the vaccines.

GMP peptides will be prepared by synthetic chemistry, purified by Reverse Phase High-Performance Liquid Chromatography (RP-HPLC), mixed in small groups (see Sect 5.2.1.2 and Appendix B; Section 7.3.4) and combined with the immune adjuvant poly-ICLC, a stabilized double-stranded RNA (see Section 2.1.2 below). The mixtures of peptides and poly-ICLC will be used for vaccination with the intention to induce cellular immune responses directed at these patient/tumor specific mutations. Each patient will receive the full complement of peptides at each immunization.

2.1.2 Poly-ICLC

2.1.2.1 TLR agonists as adjuvants for cancer vaccines

Toll like receptors (TLRs) are important members of the family of pattern recognition receptors (PRRs) which recognize conserved motifs shared by many micro-organisms, termed “pathogen-associated molecular patterns” (PAMPS). Recognition of these “danger signals” activates multiple elements of the innate and adaptive immune system. TLRs are expressed by cells of the innate and adaptive immune systems such as dendritic cells (DCs), macrophages, T and B cells, mast cells, and granulocytes and are localized in different cellular compartments, such as the plasma membrane, lysosomes, endosomes, and endolysosomes²⁴. Different TLRs recognize distinct PAMPS. For example, TLR4 is activated by LPS contained in bacterial cell walls, TLR9 is activated

CONFIDENTIAL

This document is confidential. Do not disclose or use except as authorized.

by unmethylated bacterial or viral CpG DNA, and TLR3 is activated by double stranded RNA²⁵. TLR ligand binding leads to the activation of one or more intracellular signaling pathways, ultimately resulting in the production of many key molecules associated with inflammation and immunity (particularly the transcription factor NF- κ B and the Type-I interferons). TLR mediated DC activation leads to enhanced DC activation, phagocytosis, upregulation of activation and co-stimulation markers such as CD80, CD83, and CD86, expression of CCR7 allowing migration of DC to draining lymph nodes and facilitating antigen presentation to T cells, as well as increased secretion of cytokines such as type I interferons, IL-12, and IL-6. All of these downstream events are critical for the induction of an adaptive immune response.

Among the most promising cancer vaccine adjuvants currently in clinical development are the TLR9 agonist CpG and the synthetic double-stranded RNA (dsRNA) TLR3 ligand poly-ICLC. In preclinical studies poly-ICLC appears to be the most potent TLR adjuvant when compared to LPS and CpG due to its induction of pro-inflammatory cytokines and lack of stimulation of IL-10, as well as maintenance of high levels of co-stimulatory molecules in DCs²⁶. Furthermore, poly-ICLC was recently directly compared to CpG in non-human primates (rhesus macaques) as adjuvant for a protein vaccine consisting of human papillomavirus (HPV)16 capsomeres. Poly-ICLC was found to be much more effective in inducing HPV specific Th1 immune responses²⁷.

2.1.2.2 Poly-ICLC – a synthetic TLR3 agonist with strong vaccine adjuvant properties

Poly-ICLC is a synthetically prepared double-stranded RNA consisting of polyI and polyC strands of average length of about 5000 nucleotides, which has been stabilized to thermal denaturation and hydrolysis by serum nucleases by the addition of polylysine and carboxymethylcellulose. The compound activates TLR3 and the RNA helicase-domains of MDA5 and RIG3, both members of the PAMP family, leading to DC and natural killer (NK) cell activation and production of a “natural mix” of type I interferons, cytokines, and chemokines. Furthermore, poly-ICLC exerts a more direct, broad host-targeted anti-infectious and possibly anti-tumor effect mediated by the two IFN-inducible nuclear enzyme systems, the 2'5'-OAS and the P1/eIF2a kinase, also known as the PKR (4-6), as well as RIG-I helicase and MDA5.

In rodents and non-human primates, poly-ICLC was shown to enhance T cell responses to viral antigens²⁸⁻³¹, cross-priming, and the induction of tumor-, virus-, and autoantigen-specific CD8⁺ T-cells³²⁻³⁴. In a recent study in non-human primates, poly-ICLC was found to be essential for the generation of antibody responses and T-cell immunity to DC targeted or non-targeted HIV Gag p24 protein, emphasizing its effectiveness as a vaccine adjuvant.

In human subjects, transcriptional analysis of serial whole blood samples revealed similar gene expression profiles among 8 healthy human volunteers receiving one single s.c. administration of poly-ICLC and differential expression of up to 212 genes between these 8 subjects versus 4 subjects receiving placebo³⁵. Remarkably,

CONFIDENTIAL

This document is confidential. Do not disclose or use except as authorized.

comparison of the poly-ICLC gene expression data to previous data from volunteers immunized with the highly effective yellow fever vaccine YF17D³⁶ showed that a large number of transcriptional and signal transduction canonical pathways, including those of the innate immune system, were similarly upregulated at peak time points.

More recently, an immunologic analysis was reported on patients with ovarian, fallopian tube, and primary peritoneal cancer in second or third complete clinical remission who were treated on a phase 1 study of subcutaneous vaccination with synthetic overlapping long peptides (OLP) from the cancer testis antigen NY-ESO-1 alone or with Montanide-ISA-51, or with 1.4 mg poly-ICLC and Montanide. The generation of NY-ESO-1-specific CD4⁺ and CD8⁺ T-cell and antibody responses were markedly enhanced with the addition of poly-ICLC and Montanide compared to OLP alone or OLP and Montanide³⁷.

2.1.2.3 Pre-clinical toxicology of poly-ICLC

Complete information on the pre-clinical toxicology studies can be found in the poly-ICLC (Hiltonol®) Investigator Brochure (IB). The results of these toxicology studies are summarized in brief below:

Single dose toxicity:

All administrations of poly-ICLC were intravenous (IV).

Rodents. The median lethal dose (LD50) values for single dose poly-ICLC were approximately 15-18.3 mg/kg in rats and 25-30 mg/kg in mice. No necropsies were conducted.

Dogs. In beagle dogs, the lethal dose of single dose poly-ICLC administration was 4.0 mg/kg. Necropsy indicated toxic effects in the gastrointestinal, hepatic, cardiovascular, renal, endocrine, and lymphatic systems. Sublethal doses caused reversible nephrotoxicity and hepatotoxicity. The non-toxic dose for dogs was 0.25 mg/kg.

Primates. In rhesus monkeys, single-dose administration of poly-ICLC was non-toxic at a dose of .5 mg/kg, but lethal at 20 mg/kg. Toxic effects were seen in the gastrointestinal, hepatic, cardiovascular, renal, endocrine, and lymphatic systems.

Repeated dose toxicity:

Rodents. Mice treated with four daily IV doses of up to 3.66 mg/kg poly-ICLC exhibited no toxicity.

Cats. One of two cats treated with the same regimen at 3.33 mg/kg poly-ICLC demonstrated vomiting, an episode of diarrhea, and moderate weight loss.

Non-human Primates. Three rhesus monkeys and 6 macaque monkeys were treated with 5 mg/kg IV of poly-ICLC over 2 days and 3 mg/kg 3 times weekly for 16 weeks, respectively; no significant toxicity was observed other than a single instance of emesis and shivering. Necropsy of the macaques showed no drug-related changes by gross or microscopic pathology of all organs. In two additional studies, macaque monkeys

CONFIDENTIAL

This document is confidential. Do not disclose or use except as authorized.

were treated daily with up to 3 mg/kg IV for 12 days and chimpanzees were treated daily with 3 mg/kg IV for two 6-day periods, then every other day for a total of 7 weeks. At the 3 mg/kg doses, a decrease in hematocrit was seen in both studies. No change in hematocrit was seen at 0.3 mg/kg. In the chimpanzee study, in addition to a decrease in hematocrit, leukocytosis and elevations in alanine aminotransferase (ALT) and aspartate aminotransferase (AST) were observed and normalized after termination of dosing. No other significant toxicity was observed in these studies.

2.1.2.4 Clinical toxicology of poly-ICLC

Poly-ICLC is the TLR3 agonist formulation most extensively tested in patients with infectious diseases and in subjects with a variety of different tumor types.

Prior to the availability of recombinant interferon, poly-ICLC was used clinically at high doses $\geq 6\text{mg}/\text{m}^2$ (about 170 $\mu\text{g}/\text{kg}$) in patients with a variety of solid tumors and leukemia³⁸. Fever, often above 40°C, was a common adverse event and the primary dose-limiting factor. Other common adverse events were flu-like symptoms (nausea, vomiting, arthralgia, myalgia and fatigue) and hypotension, thrombocytopenia and leukopenia. Once recombinant interferon became clinically available, the need to pursue high dose poly-ICLC was eliminated, and it became recognized that lower doses (10 – 50 $\mu\text{g}/\text{kg}$) were highly effective at stimulating host defense and as an immune adjuvant.

By now, more than 400 patients with malignant gliomas have been entered on 7 clinical trials using low dose (1-2 mg total dose) poly-ICLC either as monotherapy or in conjunction with chemotherapy, radiation, or vaccine (Table 1). Furthermore, patients with various other solid tumors (prostate, colorectal, pancreatic, hepatocellular, breast, and ovarian cancers), in addition to patients with HIV/AIDS and multiple sclerosis have been treated on more than 10 additional clinical phase I and phase II studies. Overall, the drug has been well-tolerated across all studies and spectrum of diseases. The most common adverse events attributed as at least possibly related to poly-ICLC have included:

- bone marrow toxicity (leukopenia, neutropenia, thrombocytopenia, and anemia)
- reversible liver toxicity (AST/ALT elevations, LDH and alkaline phosphatase elevation)
- transient discomfort at the injection site
- transient fatigue/malaise
- transient flu-like symptoms

In a recently published phase I clinical trial, 11 patients with ovarian, fallopian tube, or primary peritoneal cancer were treated with poly-ICLC at a total dose of 1.4 mg in combination with Montanide-ISA-51 and synthetic over-lapping long peptides from NY-ESO-1. The vaccine was generally well-tolerated with grade 1-2 injection site

CONFIDENTIAL

This document is confidential. Do not disclose or use except as authorized.

reactions and fatigue as the only adverse events that were considered possibly or definitely drug-related³⁷. No grade 3 or 4 adverse events were reported.

In another clinical study which recently completed accrual (ClinicalTrials.gov Identifier NCT01079741) 27 patients with high-risk melanoma received poly-ICLC at a total dose of 1.4 mg in addition to NY-ESO-1 protein ± Montanide-ISA-51 given s.q. every 3 weeks for 4 doses (in addition to 6 patients who received 0.35 mg and 0.70 mg, respectively of poly-ICLC on cohorts 1 and 2 of the dose escalation part of the trial). The vaccine was generally well-tolerated with grade 1 and 2 injection site reactions and transient, grade 1 or 2, flu-like symptoms that resolved after 12-48 hours [REDACTED]

Table 1 Clinical Trials with Low-Dose poly-ICLC

Protocol Title	Phase	Protocol Location	Indication	Status	N	Active	Year of initiation	Dosing Schedule
Long-term IM poly-ICLC in Malignant Glioma – an Open Pilot Study	III	Walter Reed	Malignant Glioma	Closed	67	0	1996	IM 10-50 µg/kg 1-3 X week
Poly-ICLC in Recurrent Malignant Brain Tumors, an Open Label Study	III	MCV	Recurrent Glioma	Closed	99	0	2000	IM 20 µg/kg 3 X week
Poly-ICLC in Malignant Pediatric Brain Tumors	III	L.A. Childrens Hosp	Pediatric Glioma	Closed	46	0	2002	IM 20 µg/kg 2 X week
Poly-ICLC plus Radiation in Glioblastoma	II	NABTC 2001-05	New Glioblastoma	Closed	31	0	2006	IM 20 µg/kg 3 X week
Poly-ICLC in Recurrent Anaplastic Glioma	II	NABTC 2001-06	Recurrent Anaplastic Glioma	Closed	55	6	2006	IM 20 µg/kg 3 X week
Poly-ICLC plus Temodar in Newly Diagnosed Glioblastoma	II	NABTT 2005-01	New Glioblastoma	Closed	97	24	2006	IM 20 µg/kg 3 X week
Pilot Study of MUC1 Vaccine plus poly-ICLC in Advanced Prostate Cancer	III	UPMC05-086	Advanced Prostate Cancer	Open	25	15	2006	IM 25 µg/kg 2 X week
Poly-ICLC plus Dendritic Cell vaccine in Recurrent Gliomas	I	UPMC	Recurrent malignant gliomas	Open	25	20	2007	IM 20 mcg/kg
Poly-ICLC plus HSP-HPVE7 Vaccine in Cervical Dysplasia	I	Nventa	Cervical Dysplasia	Closed	24	5	2007	.05 – 2 mg
IntraTumoral poly-ICLC plus Radiation and TACE in Liver Cancer	I	UMDNJ	Hepatoma, Metastatic pancreatic cancer	Open	31	1	2007	.25-2 mg

CONFIDENTIAL

This document is confidential. Do not disclose or use except as authorized.

Table 1 Clinical Trials with Low-Dose poly-ICLC								
A Randomized Controlled Phase I dose escalation trial of Nasal Hiltonol in normal volunteers.	I	NIAID, NIH:	Normal volunteers	Closed	56	0	2009	.25-4mg IN
PSMA and TARP peptide with poly ICLC adjuvant in ... Prostate Cancer.	I/II	Moffit Cancer Center	Prostate Cancer	Open	30		2009	1 mg
CDX 1307 vaccine with poly-ICLC in metastatic cancers	I	Various	Metastatic Cancers	Closed	20		2009	2 mg IM
Poly-ICLC with glioma associated peptide vaccine	I/II	UPMC	Grade II Gliomas	Open	20		2009	20 mcg/kg IM 2X Wk
MUC1 Hundred-mer and poly-ICLC Vaccine for Triple-Negative Breast Cancer.	I/II	Case Western	Triple negative breast cancer	Open	37		2009	50 mg IM
MUC1 100-mer and poly-ICLC Vaccine for Colonic Polyposis	I/II	UPMC	Colonic Adenoma	Open	45		2009	.5 mg SC
Hiltonol +NYESO1 Protein Vaccine in Ovarian Cancer	I/II	MSKCC, LICR	Ovarian Cancer	Closed	28	0	2009	1.4 mg SC

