6.1 Anticipated Toxicities

A list of the adverse events and potential risks associated with the agents administered in this study appears below and will determine whether dose delays and modifications will be made or whether the event requires expedited reporting **in addition** to routine reporting.

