6.1.1 Adverse Events for poly-ICLC

Poly-ICLC is an investigational agent; however there has been significant experience in previous clinical trials as discussed in 2.1.2.4. The safety profile has been acceptable.

These reactions have been generally mild to moderate and transient for most patients in previous studies.

CONFIDENTIAL

This document is confidential. Do not disclose or use except as authorized.

Localized reactions:

- Transient (<24 h) injection fluid accumulation
- Erythema
- Induration
- Pruritus
- Edema
- Localized rash

Systemic reactions:

Flu-like symptoms including malaise, fatigue, myalgia/arthralgia, headache, fever and chills.

Hepatobiliary Disorders:

- Alanine aminotransferase (ALT) increased
- Aspartate aminotransferase (AST) increased
- Lactate dehydrogenase (LDH) elevated
- Alkaline Phosphatase increased

Bone Marrow:

- Transient Leukocyte count decreased, Neutrophil count decreased, Platelet count decreased, and Anemia

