6.1.2 Adverse Events for Personalized NeoAntigen Peptides

Localized reactions or systemic reactions are not expected, but may occur:

Localized reactions:

- Erythema
- Induration
- Pruritus
- Edema
- Localized rash

Systemic reactions:

Flu-like symptoms including malaise, fatigue, myalgia/arthralgia, headache, fever and chills.

Autoimmune diseases:

CONFIDENTIAL

This document is confidential. Do not disclose or use except as authorized.

This is a theoretical possibility for which patients will be monitored. In principle, the mechanisms that allow the immune system to recognize tumor antigens could also lead to breakdown of tolerance to native or self-antigens, generating an autoimmune reaction.

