11 ADVERSE EVENT REPORTING REQUIREMENTS

11.1 Definitions

11.1.1 Adverse Event (AE)

An adverse event (AE) is any undesirable sign, symptom or medical condition or experience that develops or worsens in severity after starting the first dose of study treatment or any procedure specified in the protocol, even if the event is not considered to be related to the study.

Abnormal laboratory values or diagnostic test results constitute adverse events only if they induce clinical signs or symptoms or require treatment or further diagnostic tests.

CONFIDENTIAL

This document is confidential. Do not disclose or use except as authorized.

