14.4 Analysis of Safety and Toxicity Data

Analysis set and grouping for the analyses: All patients who receive one or more doses of NeoVax will be included in the safety analysis. All listings and tables will be presented by dose level.

Adverse events (AEs): All adverse events recorded during the study will be summarized. The incidence of treatment emergent adverse events will be summarized by dose level according to primary system organ class, severity based on the National Cancer Institute's Common Terminology Criteria for Adverse Events (CTCAE) version 4.0, type of adverse event, and relationship to the vaccine. Deaths reportable as SAEs and non-fatal serious adverse events will be listed by patient and tabulated by primary system organ class, type of adverse event, and dose level.

DLTs will be listed and their incidence summarized by primary system organ class, worst grade based on the CTCAE version 4.0, type of adverse event, and by dose level. Any other information collected (e.g. start/end dates and duration of adverse event, severity or relatedness to study medication) will be listed, as appropriate.

Laboratory abnormalities: All laboratory values will be converted into SI units, as appropriate, and the severity grade calculated using CTCAE, version 4.0. Parameters for which a grading does not exist will be classified into low/normal/high group by means of laboratory normal ranges. For each laboratory test (e.g., hematology, biochemistry) a listing of laboratory values will be provided by laboratory parameter, patient and treatment group. The frequency of notable lab abnormalities (i.e., newly occurring CTCAE grade-3 or -4 laboratory toxicities), will be displayed by parameter, cycle, and dose level. Similarly, the frequency of all laboratory abnormalities will be displayed by parameter, worst CTCAE version 4.0 grade experienced and dose level. A separate listing will display notable laboratory abnormalities (i.e., newly occurring CTCAE grade-3 or -4 laboratory toxicities). Laboratory data will be summarized by presenting grade shift tables for those parameters for which CTCAE version 4.0 allows classification. All remaining data will be summarized by presenting shift tables based on normal ranges.

Laboratory data will be also be displayed by presenting summary statistics of raw data and change from baseline values (means, medians, standard deviations, ranges).

CONFIDENTIAL

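### LDH elevation is a listed liver toxicity of poly-ICLC, but no scheduled test measures LDH, so the safety analysis can neither show nor exclude a rise

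*Combined protocol and SAP*

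**What the plan says.** Safety is a primary objective (section 1.2): "To evaluate safety and tolerability of administering NeoVax in patients with high-risk melanoma". Two places name the liver laboratory effects expected of poly-ICLC. Section 2.1.2.4 lists "reversible liver toxicity (AST/ALT elevations, LDH and alkaline phosphatase elevation" among the most common events at least possibly related to the drug. Section 6.1.1, under hepatobiliary disorders, gives the same four analytes, one entry being "Lactate dehydrogenase (LDH) elevated". Section 6.1 gives the list a working role: it "will determine whether dose delays and modifications will be made or whether the event requires expedited reporting".

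The study calendar marks serum chemistry at both screenings, at every visit from day 1 to day 190, and in long-term follow-up. Footnote 6 defines the panel, and LDH is not in it.

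For laboratory results, section 14.4 plans displays by dose level, shift tables and more: "Laboratory data will be also be displayed by presenting summary statistics of raw data and change from baseline values". It also provides for analytes without a toxicity grade: "Parameters for which a grading does not exist will be classified into low/normal/high group by means of laboratory normal ranges".

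On autoimmune disease, section 6.1.2 says: "This is a theoretical possibility for which patients will be monitored". It names no method. The calendar's autoimmune panel (footnote 4: ANA, anti-thyroglobulin antibodies, rheumatoid factor) has one mark, at initial screening.

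**The concern.** The protocol names a laboratory toxicity of its adjuvant, twice, and then schedules no test that could detect it. Section 14.1 makes the recommended dose of poly-ICLC part of the primary goal, and under section 5.4.1 poly-ICLC is the only component whose dose changes between Cohort 1 and Cohort -1. An expected effect of that component should be observable at each dose level.

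As written, silence about LDH in the final report would mean that it was not measured. A reader who sees LDH in the anticipated-toxicity list and no LDH finding in the results could easily take it to mean that no rise occurred.

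**Working it through.** No sample size, power or error rate bears on this point, and the plan gives no figure to reproduce. The check sets the toxicity lists beside the calendar and counts scheduled measurements.

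**1. Listed against measured.** Sections 2.1.2.4 and 6.1.1 name the same four liver analytes. Footnote 6 has 11 analytes, counting total and direct bilirubin separately: glucose, urea nitrogen, creatinine, sodium, potassium, calcium, total bilirubin, direct bilirubin, AST, ALT, alkaline phosphatase.

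| Named liver analyte | In the footnote 6 panel |
|---|---|
| AST | yes |
| ALT | yes |
| Alkaline phosphatase | yes |
| LDH | no |

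Result: 3 of 4 measured.

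**2. Other routes to an LDH value.** The remaining scheduled laboratory rows are the blood count, pregnancy test, infectious panel, autoimmune panel and HLA typing, plus blood draws for sequencing and immune monitoring. None includes LDH. The organ-function limits in sections 3.1.1.9 and 3.1.2.2 do not include it either, and sections 5.2.3.1 and 5.2.3.2 apply the 3.1.1.9 limits before each dose.

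**3. Draws at which LDH could have been added.** The chemistry row is marked at initial screening (1), at second screening (1) and on days 1, 4, 8, 15, 22, 29, 50, 78, 85, 106, 134, 141, 162 and 190 (14). That is 1 + 1 + 14 = 16 draws up to day 190, or 15 if second screening is done on day 1 as footnote 19 permits. Long-term follow-up adds more. Scheduled LDH values: 0.

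**4. Whether adverse event reporting fills the gap.** Section 11.1.1 states: "Abnormal laboratory values or diagnostic test results constitute adverse events only if they induce clinical signs or symptoms or require treatment or further diagnostic tests". A silent LDH rise would not be an adverse event, and without a scheduled test it would not be seen. Unscheduled tests are possible, but they would be selective and could not give a rate by dose level.

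**5. What section 14.4 can compute.** A shift or change from baseline needs one baseline value and at least one later value. From scheduled data LDH has 0 and 0. The rule for ungraded parameters means the analysis plan could take LDH without amendment if it were measured.

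**6. Autoimmune panel.** One scheduled draw before vaccination and none at any later visit, against seven planned doses (five priming, two boost; section 5.3). The peptide ELISAs in section 8.1.3 measure antibodies to the immunizing peptides, so they do not substitute. No change in these three serologies can be computed from scheduled data.

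**The case against.** The best case for the plan is that nothing decisive depends on LDH. The dose-delay rules in section 6.3 work by grade and attribution and name no LDH threshold. The cohort and stopping rules count dose-limiting toxicities. Section 11.1.3.1 uses section 6.1 as the list of expected events, so listing LDH there has a purpose even without an assay. Whether CTCAE grades LDH is not stated in the documents; if it does not, an LDH value could not meet the grade 3 or 4 laboratory criterion in section 5.5. All of this stands, and it limits the importance of the gap. It does not remove the mismatch between the toxicity list and the calendar, or the loss of information from the safety dataset.

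Three stronger readings are tempting, and the documents do not support them.

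- A reader might infer that liver toxicity goes unmonitored. It does not: AST, ALT, alkaline phosphatase and both bilirubins are measured throughout.
- A reader might infer that section 14.4 will produce empty tables. It summarizes the tests collected and names neither LDH nor autoantibodies, so no such table is promised.
- A reader might infer that autoimmunity is unmonitored, or that the screening panel is a failed baseline. Section 6.1.2 promises monitoring but not serology. History, physical examination and adverse event evaluation are scheduled at each treatment and follow-up visit, with repeated blood counts, creatinine, glucose and liver tests. A single screening draw fits exclusion 3.2.10 on autoimmune disease, just as the infectious panel, also drawn once, fits exclusion 3.2.12.

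Repeating autoantibodies in about 15 uncontrolled patients is a debatable preference, because incidental positives would be hard to interpret.

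**Conclusion.** The LDH mismatch holds. One of the four liver laboratory toxicities that the protocol names for poly-ICLC has no scheduled value before or after any dose, so an LDH rise can be neither shown nor excluded at either dose level. The size is one analyte. General hepatotoxicity monitoring is intact, and no sample size, stopping rule or operating characteristic changes.

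The conclusion assumes that footnote 6 is the complete chemistry panel, as the calendar presents it, and that sites do not routinely add LDH outside the protocol. The footnote is plain text, so an error in reading the table is an unlikely explanation.

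The autoimmune point is a secondary note: the monitoring commitment in section 6.1.2 has no stated method and should be reconciled with the calendar.

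**What to change.** Add LDH to the footnote 6 panel at screening and at the existing chemistry draws. Summarize it by dose level in the section 14.4 laboratory tables, as low, normal or high if no CTCAE grade applies. The cost is one more analyte on blood already drawn, plus some follow-up of incidental abnormal values. For patients already treated without it, the report should say that LDH was not measured.

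For autoimmunity, state in section 6.1.2 or the calendar how the promised monitoring is done. If the panel stays at screening only, the report should not claim an absence of new autoantibodies, because none are scheduled after vaccination. This costs only text.
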